10. POPULATION PHARMACOKINETIC (POPPK) ANALYSES

Population pharmacokinetic analyses will be conducted under the direction of CPMS, Quantitative Sciences, GSK. The data from this study may be combined with the data from other studies for a population PK analysis, which will be reported separately.

11. PHARMACODYNAMIC (AND/OR BIOMARKER) ANALYSES

Pharmacodynamic and biomarker analyses are not within the scope of this reporting and analysis plan. Any planned analyses will be described in a separate document.

12. PHARMACOKINETIC / PHARMACODYNAMIC ANALYSES

Further exploratory pharmacokinetic/pharmacodynamic analyses are not within the scope of this SAP. Any planned analyses will be described in a separate document.

15. APPENDICES

15.1. Appendix 1: Exclusions from Per Protocol Population

A per-protocol population for this study is not defined and not planned.

15.2. Appendix 2: Schedule of Activities

Refer to protocol for schedule of events.

15.3. Appendix 3: Assessment Windows

15.3.1. Definitions of Assessment Windows for Analyses

Visit collected in the data will be used for the analysis and no visit window assigned for the study. Tumor response measurements from unscheduled visits will be included as well as most extreme result reporting (e.g. worst grade post-baseline).

15.4. Appendix 4: Study Phases

15.4.1. Study Phases for Treatment

Assessments and events will be classified according to the time of occurrence relative to first dose of study treatment.

Treatment Phase	Definition
Pre-therapy	Time prior to the subject's first dose of study treatment.
On-therapy	Time from first dose of study treatment to the last dose date of study treatment +
	30 days.
Post-therapy	Time beyond the on-therapy period

15.4.2. Study Phases for Concomitant Medication and Blood and Blood Supportive Care Products

Concomitant medication and blood and blood supportive product start and end dates will be assigned to study time periods in relation to first dose of study treatment as defined below. The start date references time flag variables and end date reference time flag variables will be added to the concomitant medications and blood and blood supportive products datasets, respectively.

15.4.2.1. Start Date Relative to Treatment:

Treatment State	Definition
	Start Date < Study Treatment Start Date
	OR
Defens	Study Treatment Start Date is missing (i.e., subject has not taken any study
Before	treatment)
	OR
	Start Date is missing and Stop Date < Study Treatment Start Date
During	Study Treatment Start Date <= Start Date < Study Treatment Stop Date + 30
	days
	OR
	Study Treatment Stop Date is missing
	OR
	Start Date is missing and Stop Date >= Study Treatment Start Date
After	Start Date > Study Treatment Stop Date + 30 days

Treatment State	Definition
Before	Stop Date < Study Treatment Start Date OR Study Treatment Start Date is missing (i.e., subject has not taken any study treatment)
During	Study Treatment Start Date <= Stop Date < Study Treatment Stop Date + 30 days OR Study Treatment Stop Date is missing OR End Date is missing and Start Date relative to treatment is not "After"
After	Start Date > Study Treatment Stop Date + 30 days OR End Date is missing and Start Date relative to treatment='AFTER'

15.4.2.2. Stop Date Relative to Treatment:

15.4.2.3. Blood and Blood Supportive Care Products

Only on-therapy blood and blood supportive care products that start after the start of study treatment are included in the Blood Products and Blood Supportive Care Product summaries. Therefore, for summary tables, include blood and blood supportive care product records where start relative to treatment in ('DURING') and end relative to treatment in ('DURING'). All data will be reported in listings.

15.4.2.4. Summary of Concomitant Medication

Concomitant medication start relative to treatment and end relative to treatment flags are used to select data to include in the concomitant medication summaries as follows:

 Summary of Concomitant Medications: This summary will contain medications including those with start date prior to study treatment start and continue (missing end date or end date after study treatment start date) on therapy. Note that any medications with start date and end date prior to study treatment start date will be excluded. In addition, any medication that was started during post-therapy will be excluded. Include concomitant medication records where start relative to treatment in ('BEFORE','DURING') and end relative to treatment in ('DURING','AFTER').

15.5. Appendix 5: Data Display Standards & Handling Conventions

15.5.1. Reporting Process

Software

C ontribution				
• The currently supported versions of SAS software 9.3 or higher version will be used.				
Reporting Area				
HARP Server	: [Insert Server]			
HARP Area	: [Insert Area & Reporting Effort]			
QC Spreadsheet	: [Insert Location]			
Analysis Datasets				
 Analysis datasets will be created according to CDISC/ADaM standards. 				
• For creation of ADaM datasets (ADCM/ADAE), the same version of dictionary datasets				
will be implemented for conversion from SI to SDTM.				
Generation of RTF Files				
RTF files will be generated for all analyses.				

15.5.2. Reporting Standards

General						
• The current GSK Integrated Data Standards Library (IDSL) will be applied for reporting,						
unless otherwise stated:						
4.03 to 4.23: General Principles						
 5.01 to 5.08: Principles Related to Data Listings 						
 6.01 to 6.11: Principles Related to Summary Tables 						
 7.01 to 7.13: Principles Related to Graphics 						
Formats						
All data will be reported according with the All Treated Population, according to the						
actual treatment the subject received unless otherwise stated.						
 GSK IDSL Statistical Principles (5.03 & 6.06.3) for decimal places (DP's) will be adopted 						
for reporting of data based on the raw data collected.						
 Numeric data will be reported at the precision collected on the eCRF. 						
The reported precision from non eCRF sources will follow the IDSL statistical principles.						
Planned and Actual Time						
 Reporting for tables, figures and formal statistical analyses : 						
 Planned time relative to dosing will be used in figures, summaries, statistical 						
analyses and calculation of any derived parameters, unless otherwise stated.						
 The impact of any major deviation from the planned assessment times and/or 						
scheduled visit days on the analyses and interpretation of the results will be						
assessed as appropriate.						
Reporting for data listings:						
Planned and actual time relative to study drug dosing will be shown in listings						
(Refer to IDSL Statistical Principle 5.05.1).						
Unscheduled Visits						
Unscheduled visits will not be included in summary tables except for most extreme						
result reporting (e.g. worst grade post-baseline), as well as tumor assessments.						

	Unscheduled visits will not be included in figures except for tumor assessments.						
	All unschedu	All unscheduled visits will be included in listings.					
De	Descriptive Summary Statistics						
1.	Continuous Data	1. Refer to IDSL Statistical Principle 6.06.1					
1.	Categorical Data	2. N. n. frequency. %					

15.5.3. Reporting Standards for Pharmacokinetic

Pharmacokinetic Cor	Pharmacokinetic Concentration Data					
PC Windows Non-	PC WNL file (CSV format) for the non compartmental analysis by Clinical					
Linear (WNL) File	Pharmacology Modelling and Simulation function will be created according					
	to VQD-SOP-005939.					
	Note: Concentration values will be imputed as per GUI_51487					
Descriptive	Refer to IDSL PK Display Standards.					
Summary	Refer to IDSL Statistical Principle 6.06.1.					
Statistics,	Note: Concentration values will be imputed as per GUI_51487 for descriptive					
Graphical Displays	summary statistics/analysis and summarized graphical displays only.					
and Listings						
NONMEM/Pop PK	Not applicable.					
File						
NONMEM/PK/PD	Not applicable.					
File						
Pharmacokinetic Parameter Derivation						
PK Parameter to be	The following PK parameters will be derived by the Programmer : Cmax,					
Derived by	Tmax, Ctrough, AUC0-t, AUC0-tau, AUCinf, t½, λz , TI, AR, C12 or C24,					
Programmer	Ae(0-x) or Ae(0-∞), CLr					
Pharmacokinetic Para	ameter Data					
Is NQ impacted PK						
Parameters Rule	No.					
Being Followed						
Descriptive	Refer to IDSL PK Display Standards.					
Summary	Refer to GSK Data Standards and statistical principles					
Statistics,						
Graphical Displays						
and Listings						

15.6. Appendix 6: Derived and Transformed Data

15.6.1. General

Multiple Measurements at One Time Point

All data will be reported according to the nominal visit date for which it was reported (that is, no visit windows will be applied during dataset creation). Unscheduled data will only be included in the display sections that report most extreme result (e.g. worst grade post-baseline).

If multiple assessments on different days are reported for the same scheduled assessment, then the latest assessment for that scheduled assessment will be analyzed.

If multiple assessments are reported on the same date for the same scheduled planned time, then the worst-case result will be analyzed, with the exception of laboratory data reported from both central and local laboratories.

ECG values will be measured in triplicate: 3 assessments are collected for each scheduled planned time, the first 3 measures will be used to compute the mean values for ECG intervals at each scheduled planned time. For qualitative ECG measures (Normal, Abnormal, Not Clinically Significant, Abnormal, Clinically Significant) and QTcF grade, the most clinically significant value (highest grade) will be summarized.

Subjects having both High and Low values for Normal Ranges at any post-baseline visits for safety parameters will be counted in both the High and Low categories of "Any visit post-baseline" row of related summary tables.

Data from all assessments (scheduled and unscheduled), including multiple assessments, will be included in listings.

Study Day

Reference Dates

Unless otherwise stated, the safety reference (start) date will be the start of treatment of GSK3326595. This will also be the efficacy reference date for this study. The reference date for baseline characteristics (e.g. age) will be the date of screening.

Study Day for Safety Measures/Efficacy

If the date of interest occurs on or after the safety/efficacy reference date then the safety/efficacy study day will be calculated as (date of interest – safety/efficacy reference date) + 1. If the date of interest occurs before the safety/efficacy reference date then the safety study day will be calculated as (date of interest-safety/efficacy reference date). There is no safety/efficacy study day 0.

Duration of Elapsed Time

Durations (e.g., the duration of an AE, duration of exposure, etc.) are calculated as the stop date minus the start date plus one.

For elapsed time (e.g., the time since initial diagnosis):

If the reference date is on or after the event date, then the elapsed time is the reference date minus the event date + 1.

If the reference date is before the event date then the elapsed time is the reference date minus the event date.

When reporting time to event (TTE) durations in months, divide the number of days by 30.4375; to report in weeks divide the number of days by 7; to report in years divide the number of days by 365.25. These algorithms for time to event return decimal numbers, and ignore the actual numbers of days in the months or years between start date and stop date. The "year" used in these algorithms is 365.25 days long, and the "month" is one twelfth of that year.

For converting all other durations (e.g., duration of adverse events, duration of exposure, age) to weeks, months or years use the following:

To report the duration in weeks, divide the number of days by 7.

To report the duration in months, use:

(YEAR(stopdate + 1) - YEAR(startdate)) * 12 + (MONTH(stopdate + 1) - MONTH(startdate) - 1) + (DAY(stopdate + 1) > = DAY(startdate))

To report the duration in years use:

INTCK('year', startdate, stopdate + 1) - (MONTH(stopdate + 1) < MONTH(startdate) or (MONTH(stopdate + 1) = MONTH(startdate) and DAY(stopdate + 1) < DAY(startdate)))

The algorithms above for age and duration return whole numbers for months and years, accurately accounting for the actual numbers of days in the months or years between the start date and the stop date.

15.6.2. Study Population

Demographics

Age
GSK standard IDSL algorithms will be used for calculating age where birth date will be
imputed as follows:
 Any subject with a missing day will have this imputed as day '15'.
 Any subject with a missing date and month will have this imputed as '30th June'.
 Birth date will be presented in listings as 'YYYY'.
Body Mass Index (BMI)
 Calculated as Weight (kg) / [Height (m)²
Extent of Exposure
GSK3326595
 Number of days of exposure (duration on study treatment) to study drug will be
calculated based on the formula:
Duration of Exposure in Days = Treatment Stop Date – Treatment Start Date + 1
 Participants who were randomized but did not report a treatment start date will be
categorised as having zero days of exposure.
 The cumulative dose will be based on the formula:
Cumulative Dose = Sum of (Number of Days x Total Daily Dose)
If there are any treatment breaks during the study, exposure data will be adjusted accordingly.
Pembrolizumab
 Extent of exposure will be calculated based on treatment cycles derived based
on cycle start dates in the exposure dataset
 Duration on study treatment will be calculated based on the formula:

Duration on study treatment = Last Treatment Stop Date – First Treatment Start Date + [lag time, e.g., Duration of Cycle]

Take into account of death date if a lag time>1, e.g., Duration of Cycle is used.

- Participants who were randomized but did not report a treatment start date will be categorised as having zero days of exposure.
- Combination Treatments (Part 3)
- Extent of exposure will be calculated for each treatment component
- Duration of treatment will be calculated based on the formula:

Duration on study treatment = Maximum of ([IV Treatment Stop Date + lag time], [Oral Treatment Stop Date]) – (Minimum of Treatment Start Date) + 1

Take into account of death date if a lag time>1, e.g., Duration of Cycle is used.

• Participants who were randomized but did not report a treatment start date will be categorized as having zero days of exposure

Actual Treatment

• Subject's actual treatment will be derived from [exposure data] [study treatment data provided by Clinical Operations]. If a subject's actual treatment is the same as assigned treatment, actual treatment is the assigned treatment; if a subject received treatment different from assigned treatment for the entire duration of treatment, actual treatment is different from assigned treatment.

15.6.3. Efficacy

Change from Baseline

Change from Baseline = Post-Baseline Visit Value – Baseline

% Change from Baseline= 100 x (Post-Baseline Visit Value – Baseline) / Baseline

Maximum Decrease from Baseline = maximum (Decrease from Baseline) prior to disease progression

If either the Baseline or Post-Baseline Visit Value is missing, Change from Baseline and % Change from Baseline is set to missing

Date of Response

For post-baseline disease assessments, the date of response (PR or better) is assigned to the latest date of disease assessments; for other response categories ([MR,] SD [or Non-CR/Non-PD], NE, PD), the date of response is assigned to the earliest date of disease assessments.

For the BOR, if BOR is SD, the latest date of SD is assigned to the date of BOR. If for other BOR responses, the earliest date of that response will be assigned as the date of BOR.

Date of New Anti-Cancer Therapy

Derived as the earliest date of new anti-cancer therapy, radiotherapy (where applicable) or cancerrelated surgical procedure (where applicable)

Missing or partial dates will be imputed for derivation of new anti-cancer therapy following rules specified in Section 15.7.3.3.

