7.1. Primary Efficacy Analyses

7.1.1. Confirmed Overall Response Rate (ORR) based on RECIST 1.1 for Part 2 (non-GBM, non-NHL) cohorts

The primary endpoint for all Part 2 cohorts, except GBM, will be overall response rate (ORR). The timepoint overall response is assessed by the investigator and recorded on the eCRF. The ORR endpoint is defined as % of subjects achieving a best response of CR and PR recorded from the start of treatment until disease progression or start of new anti-cancer therapy, whichever is earlier.

Best response will be determined programmatically based on investigator assessment at each time point. If there are two assessments, separated by not evaluable (NE) assessment(s), the best response shall be assessed applying the algorithm below, collapsing data by ignoring NE assessments. The first assessment may occur before the first planned assessment.

Confirmed responses, as outlined in RECIST 1.1 [Eisenhauer, 2009] will be summarized, as appropriate. Confirmation of response may be based on planned and/or unscheduled assessments.

The confirmed overall response rate (ORR) is defined as the ORR as per disease-specific criteria (more details in protocol Section 14.4). Subjects with unknown or missing response will be treated as non-responders, i.e., these subjects will be included in the denominator when calculating the percentage. The best overall response is a subject's best response over the time period referenced. In addition, with respect to best response:

- To be assigned a status of SD, follow-up disease assessment must have met the SD criteria at least once after the first dose for a minimum of 49 days.
- If the minimum time for SD is not met, best response will depend on the subsequent assessments. For example, if an assessment of PD follows the assessment of SD and SD does not meet the minimum time requirement the best response will be PD. Alternatively, subjects lost to follow-up after an SD assessment, not meeting the minimum time criteria, will be considered not evaluable.
- To be assigned a status of PR or CR, a confirmatory disease assessment should be performed no less than 4 weeks (28 days) after the criteria for response are first met.

The ORR will be summarized with a 2-sided 95% exact confidence interval based on the Clopper-Pearson method. The observed confirmed ORR will be reported at the interim and final analysis and will be summarized by cohort.

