BOR = best overall response; CPD = confirmed progressive disease; CR = complete response; iRECIST = immune Response Evaluation Criteria in Solid Tumors; NE = not evaluable; PR = partial response; RECIST = Response Evaluation Criteria in Solid Tumors; SD = stable disease; UPD = unconfirmed progressive disease. NOTE: "i" indicates immune responses assigned using the iRECIST evaluation criteria

^a Assume any two adjacent assessments are at least 28 days apart

^b Last assessment before the subject died/discontinued from treatment

7.2.4. Progression Free Survival (PFS) for Part 1, Part 2 (non-GBM), Part 3

Progression-free survival (PFS) will be estimated by cohorts for Part 2 as described in Section 7.1.3. RECIST 1.1 criteria will be used for non-NHL cohorts, and Lugano criteria for NHL cohorts. Estimates of 1st quartile survival, median survival, and 3rd quartile survival will be presented with 95% confidence intervals based on the Brookmeyer-Crowley method (Brookmeyer, 1982).D

7.2.5. Lesion Analysis – Parts 1, 2, and 3

Change/percent change from baseline based on the sum of target lesion diameters will be calculated by timepoint for all cohorts except NHL and GBM. Change/percent change from baseline based on the sum of target *lesion areas* will be calculated by timepoint for the *GBM cohort*. The following figures will be produced:

- Percent change from baseline in target lesions over time (spider plot) all cohorts except NHL.
- Best change from baseline in target lesions (waterfall plot) all cohorts except NHL.
- Treatment duration along with the overall response, the best change from baseline in target lesions, etc. (swimmer plot).

7.2.6. DOR and TTR for Part 2 ACC TN Cohort based on RECIST 1.1 Criteria

Duration of response (DOR) based on RECIST 1.1 for the Part 2 ACC TN cohort will be listed and summarized for subjects with a confirmed CR or PR and is defined as the time (in months) from first documented evidence of CR or PR until the first documented sign of disease progression or death, for the subset of subjects with a confirmed CR or PR. Censoring rules will follow those of the PFS analysis.

If there are a sufficient number of responders who subsequently progress or die due to PD, median DoR, first and third quartiles and 95% CI, will be estimated using the Brookmeyer-Crowley method (Brookmeyer, 1982).

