15.7.2. Handling of Missing Data

Element	Reporting Detail
General	 Missing data occurs when any requested data is not provided, leading to blank fields on the collection instrument : These data will be indicated by the use of a "blank" in subject listing displays. Unless all data for a specific visit are missing in which case the data is excluded from the table. Answers such as "Not applicable" and "Not evaluable" are not considered to be missing data and should be displayed as such. Missing data occurs when any requested data is not provided, leading to blank fields on the collection instrument Subjects with the designation of treatment relationship for adverse events (AE)s and serious adverse events (SAEs) missing will have the worst case assumed to be "Yes". There will be no other imputation for missing data other than what's described in Section 15.4.2. for partial dates and for missing exposure end dates.
Outliers	• Any subjects excluded from the summaries and/or statistical analyses will be documented along with the reason for exclusion in the clinical study report.
Responder Analysis	• For endpoints which determine the percentage of responders, subjects with unknown/not evaluable or missing best overall response will be assumed to be

Element	Reporting Detail
	non-responders, and will be included in the denominator when calculating the
	percentages.

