15.12.6. Efficacy Figures

		IDSL / Example			
NO. Chang	e in Sum of Diame	Snell ters/Areas	litie	Programming Notes	Deliverable
2.11	All Treated	RE8a	Investigator-Assessed Maximum Percent Reduction from Baseline in Sum of Diameters (RECIST 1.1 Criteria)	Part 1 one plot for QD, one for BID color/shade by dose level and indication within each	SAC
2.12	All Treated	RE8a	Investigator-Assessed Maximum Percent Reduction from Baseline in Sum of Diameters (RECIST 1.1 Criteria)	part 2 by cohort (excluding NHL , GBM)	IA, SAC
2.13	All Treated	RE8a	Investigator-Assessed Maximum Percent Reduction from Baseline in Sum of Areas (RANO Criteria)	Part 2 GBM cohort	SAC
2.14	All Treated	RE8a	Investigator-Assessed Maximum Percent Reduction from Baseline in Sum of Diameters (iRECIST Criteria)	Part 3	SAC
2.15	All Treated	custom	Spider Plot of Percent Change from Baseline in Sum of Diameters (Investigator Assessment Using RECIST 1.1 Criteria)	Part 1 one plot for QD, one for BID color/shade by dose level and indication within each	SAC
2.16	All Treated	custom	Spider Plot of Percent Change from Baseline in Sum of Diameters (Investigator Assessment Using RECIST 1.1 Criteria)	part 2 by cohort (excluding NHL, GBM)	IA, SAC

2.17	All Treated	custom	Spider Plot of Percent Change from Baseline in Sum of Areas (Investigator Assessment Using RANO Criteria)	Part 2 GBM cohort	SAC
2.18	All Treated	custom	Spider Plot of Percent Change from Baseline in Sum of Diameters (Investigator Assessment Using iRECIST Criteria)	Part 3	SAC
Time-t	o-Event	1			•
2.19	All Treated	TTE10	Graph of Kaplan-Meier Survival Curves of Progression-Free Survival with 95% Confidence Bands (Investigator Assessment using RECIST 1.1 Criteria)	by dose level for part 1, by cohort for part 2 (excluding GBM/NHL)	SAC
2.20	All Treated	TTE10	Graph of Kaplan-Meier Survival Curves of Progression-Free Survival with 95% Confidence Bands (Investigator Assessment using RANO Criteria)	GBM cohort	SAC
2.21	All Treated	TTE10	Graph of Kaplan-Meier Survival Curves of Progression-Free Survival with 95% Confidence Bands (Investigator Assessment using Lugano Criteria)	NHL cohorts	SAC
2.22	All Treated	TTE10	Graph of Kaplan-Meier Survival Curves of Progression-Free Survival with 95% Confidence Bands (Investigator Assessment using iRECIST Criteria)	Part 3	SAC
2.23	All Treated	TTE10	Graph of Kaplan-Meier Survival Curves of Overall Survival with 95% Confidence Bands	Part 2 ACC TN cohort and All ACC subjects (across parts 1/2)	SAC

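### Read literally, the SAP's maximum-decrease rule leaves a subject who progresses at the first scan with no waterfall value, and nothing else in the SAP says what to plot

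*SAP*

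**What the plan says.** SAP 15.6.3 (Efficacy) gives the only derivation of a maximum reduction in the SAP: "Maximum Decrease from Baseline = maximum (Decrease from Baseline) prior to disease progression". The next rule there is "If either the Baseline or Post-Baseline Visit Value is missing, Change from Baseline and % Change from Baseline is set to missing".

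SAP 7.2.5 (Lesion Analysis) lists the waterfall as "Best change from baseline in target lesions (waterfall plot) all cohorts except NHL" and states no assessment window. It lists the companion spider plot as "Percent change from baseline in target lesions over time (spider plot) all cohorts except NHL".

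SAP 15.12.6 specifies waterfall Figures 2.11 to 2.14 as maximum percent reduction from baseline. They cover Part 1, the Part 2 RECIST cohorts, GBM (sum of areas) and Part 3, all on All Treated. No programming note deals with subjects whose first scan is PD.

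On missing data, SAP 15.7.2 says "There will be no other imputation for missing data other than what's described" and refers to date handling. Its non-responder rule applies to percentages of responders, not to lesion measurements.

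**The concern.** If the window closes before the progression scan, a subject whose first scan is PD contributes nothing, and what is missing depends on the outcome. A subject who progresses later keeps a bar, but one taken only from scans before progression. The displays would also disagree: the same first-scan progressor would count as PD in Table 2.1 and appear in spider plot 2.16, but be absent from waterfall 2.12 without explanation.

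At stake is how a descriptive display of activity reads in single-arm cohorts. SAP 2.1 adds maximum percent reduction as a secondary analysis for Part 1. SAP 3.1.9 uses it in the Part 2 interim analysis intended for publication, and Figure 2.12 is marked as an interim deliverable.

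**Working it through.** The plan states no figure for this variable, so there is nothing to reproduce. The check applies the rule to records and then works out the direction and possible size of the effect.

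**Step 1: the rule on five invented records.** Values are percent change in the target-lesion sum.

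| Record | Scans in order | Strictly before PD | Up to and including PD |
|---|---|---|---|
| A | −10 (SD), −35 (PR), −5 (PD) | −35 | −35 |
| B | +45 (PD) | none | +45 |
| C | +8 (SD), +30 (PD) | +8 | +8 |
| D | −12 with a new lesion (PD) | none | −12 |
| E | +25 (PD) | none | +25 |

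The two readings differ only for first-scan progressors. The plotted share with shrinkage is 1 of 2 (50%) under the strict reading and 2 of 5 (40%) under the inclusive one.

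**Step 2: direction.** Let N subjects have a post-baseline measurement and s of them show shrinkage. Let k be first-scan progressors, of whom d have shrinking targets (PD by new lesion). The full share is s/N and the displayed share is (s − d)/(N − k). The displayed share is larger when (s − d)N > s(N − k), that is, when d/k < s/N. So the plot overstates shrinkage when shrinkage is rarer among first-scan progressors than overall. That is expected when first-scan PD is mainly by target growth.

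**Step 3: size over an assumed range.** Take N = 50, s = 20 (40%) and d = 0:

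- k = 5 (10%): 20/45 = 44%
- k = 10 (20%): 20/40 = 50%
- k = 15 (30%): 20/35 = 57%
- k = 20 (40%): 20/30 = 67%

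The offset at k = 10: with d = 2, 18/40 = 45%; with d = 4, 16/40 = 40%, which is no distortion.

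**Step 4: an illustration from the plan's own GBM rates.** Inputs are six-month PFS of 17% (null) and 35% (of interest) from Protocol 11.3, scans every 8 weeks from Protocol 8.7.2, and a maximum of 28 subjects. Assuming exponential PFS, the probability of progression or death by day 56 is 1 − PFS6^(56/182.6).

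- 17%: 1 − 0.17^0.307 = 0.419, about 12 of 28
- 35%: 1 − 0.35^0.307 = 0.275, about 8 of 28

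If all of these were left out and none had shrinkage, the displayed share would be multiplied by 1/(1 − 0.419) = 1.72 or 1/(1 − 0.275) = 1.38. These factors are upper limits, because subjects who die or deteriorate without a scan have no bar under any rule.

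**Step 5: Part 3.** Under SAP 7.2.3, a first progression is unconfirmed (iUPD), and later stable disease or response can still be assigned. If progression in 15.6.3 means confirmed progression (iCPD), the iUPD scan comes before it and supplies a bar. If it means iUPD, a subject with iUPD at the first scan has no value, even if a response follows. The SAP does not choose.

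**The case against.** The strongest reply is that the SAP nowhere says these subjects are excluded. SAP 7.2.5 sets no cut-off. The figures use the sponsor's shell RE8a, whose handling of a subject with only a PD scan cannot be seen. The 15.6.3 line defines a decrease while the figures plot a percent reduction, and the section still carries unresolved template brackets.

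There is also a benign reading. Best response in SAP 7.1.1 is "recorded from the start of treatment until disease progression", yet PD can itself be the best response there. A cut-off at progression also has a proper purpose, since Protocol 5.4.1 allows treatment beyond progression and later scans should not count. All of this stands. It shows that exclusion follows from literal wording plus silence, and that a programmer could read the line inclusively. It does not show that the wording is adequate, because two competent programmers could produce different figures.

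A reader might also infer that no RECIST bar could reach +20%. That does not hold. RECIST progression on target lesions also needs an absolute increase of 5 mm (Protocol 14.4.1.4.1), and 20% of 25 mm is 5 mm. Any baseline sum below 25 mm can therefore grow by more than 20% without PD: 16 mm to 20 mm is +25% but only 4 mm.

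**Conclusion.** The point holds as a defect of definition. On its plain wording, 15.6.3 gives no value to a first-scan progressor in Figures 2.11 to 2.13. For Figure 2.14 the outcome turns on iUPD or iCPD. No other SAP provision fills the gap.

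A reader might go further and conclude that the SAP drops these subjects and that the published waterfalls do overstate shrinkage. The documents do not support that: they state no exclusion, and they give no first-scan progression rates or split between target growth and new lesions. The 44% to 67% range and the GBM factors of 1.38 and 1.72 show what could happen under stated assumptions and are not estimates for this trial. Nor does SAP 2.1 declare this analysis for every part; it names Part 1.

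The reach is limited. The SAP tabulates neither a share with shrinkage nor a median best change. Response tables keep subjects with missing response in the denominator, and spider plots use every time point. ORR, PFS and the cohort decision rules do not use this variable.

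**What to change.** - In SAP 15.6.3, define best percent change as the smallest percent change from baseline in the sum of diameters (sum of areas for GBM) over all post-baseline assessments up to and including the first assessment of progression, and before any new anti-cancer therapy.
- State whether iUPD or iCPD closes the window in Part 3.
- Use the same term and window in 7.2.5 and in the titles of Figures 2.11 to 2.14.
- Footnote each waterfall with the number of All Treated subjects without a bar and the reason, such as no post-baseline scan or, in Part 1, where Protocol 5.1 does not require measurable disease, no target lesions.

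The cost is a short wording change and a small programming change. The downside is that the figures become slightly less favourable.
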